1. INTRODUCTION

The purpose of this SAP is to describe the planned analyses to be included in the Clinical Study Report for Study 213497.

Descriptive study population analyses such as summary of demography and baseline characteristics and additional detail with regards to data handling conventions and the specification of data displays (including COVID-19 reporting) will be provided in the Output and Programming Specification (OPS) document.

1.1. Objectives, Estimands and Endpoints

1.1.1. Objectives and Endpoints

1.1.1.1. Parts A and B (Healthy participants)

[figure not shown]
[figure not shown]
[figure not shown]
Objectives	Endpoints

Primary
 
 To evaluate the safety and tolerability of GSK3923868 following single and repeat inhaled administration in healthy participants. 	
 Adverse events (AEs) and serious adverse events (SAEs). Clinically significant laboratory values, vital signs, 12-lead electrocardiogram (ECG) and spirometry measurements up to Day 2 of the final treatment period in Part A, and Day 18 in Part B.

Secondary
 
 To evaluate the plasma pharmacokinetics of GSK3923868 following single and repeat inhaled administration in healthy participants. 	
Derived pharmacokinetic parameters as data permit, including (but not limited to):
 
Single dose (Part A, Cohorts 1 & 2):
 
 Area under the plasma GSK3923868 concentration versus time curve from time zero to last quantifiable concentration (AUC(0-t)) and from time zero to infinity (AUC(0-∞)) (if determined). Maximum observed GSK3923868 plasma concentration (Cmax). Time to maximum observed plasma drug concentration (Tmax). 
Repeated dose (Part B, Cohorts 3 & 4):
 
 AUC(0-τ) on Day 1 and Day 14 ($\tau=24\text{h}$ for once a day dosing regimen) (if determined). Cmax and Tmax on Day 1 and Day 14.

Objectives	Endpoints
CCI	

1.1.1.2. Part C (Participants with Asthma)

Objectives	Endpoints
Primary	
• To evaluate the safety and tolerability of GSK3923868 following repeat inhaled administration in participants with asthma.• AE and SAEs• Clinically significant laboratory values, vital signs, 12-lead ECG and spirometry measurements up to Day 8.
Secondary	
To evaluate the plasma pharmacokinetics of GSK3923868 following repeat inhaled administration in participants with asthma.
 
• AUC(0-τ) on Day 1 and Day 7 ($\tau=24h$ for once a day dosing regimen) (if determined).• Cmax and Tmax on Day 1 and Day 7.

1.2. Study Design

Overview of Study Design and Key Features	
Part A: Single Ascending Dose Healthy Participants  
Part A: Single Ascending Dose Healthy Participants
 
Cohort 1: n=12 (9A:3P)
 
Cohort 2: n=12 (9A:3P)
 
TP: Treatment Period inclusive of sentinel dosing group (1A:1P)
 
A: Active P: Placebo
	
Part B: Repeat Dose Healthy Participants  
Part B: Repeat Dose Healthy Participants
 
Cohort 3: n=8 (6A:2P)
 
Cohort 4: n=8 (6A:2P)
 
14-Day Repeat Dose
 
14-Day Repeat Dose
 
Follow Up (7 to 14 days post last dose)
 
A: Active P: Placebo
	
Part C: Repeat Dose Participants with Asthma  
Part C: Repeat Dose Participants with Asthma
 
Cohort 5: n=16 (12A:4P)
 
7-Day Repeat Dose
 
Follow Up (7 to 14 days post last dose)
 
A: Active P: Placebo
	
Design Features	
A randomized double-blind, placebo controlled, three-part (Parts A, B and C), First Time in Human (FTIH) study to assess safety, tolerability and pharmacokinetics of GSK3923868 inhalation powder
 
In Part A, single ascending doses of GSK3923868 will be assessed in two sequential crossover cohorts (Cohorts 1 and 2, 12 participants per cohort) of healthy participants, each with up to three treatment periods. There will be a minimum of 10 days between doses, before a follow up visit 7-14 days post the final dose.

Overview of Study Design and Key Features																					
	
Part B will assess repeat doses of GSK3923868 for 14 days across two parallel cohorts (Cohorts 3 and 4) of 8 healthy participants (total 16 participants in Part B).
 
In Part C, further repeat dosing of GSK3923868 for 7 days will be assessed in a single parallel cohort (Cohort 5) of 16 participants with stable asthma. Part C will be randomized according to two strata:1) SABA and/or intermittent ICS/LABA users and 2) ICS or ICS/LABA users.
 
A Dose Escalation Committee (DEC) will be responsible for the review of emerging safety, tolerability and plasma PK results to determine the progression of single ascending dose levels in each treatment period in Part A and the progression to repeat dose levels in Parts B and C.
																				
Study intervention	
The starting dose in Part A Cohort 1 Period 1 is 50 mcg.
 
The planned doses for dose escalation in Part A after the first cohort with 50 mcg are 100, 250, 500, 1000, and 3000 mcg. The planned dose for Part B (Cohorts 3 and 4) and Part C is 3000 mcg.
 
  
 Part	Screening	Treatment Period	Washout Period	Follow-Up	
   
 A	Up to 30 days before the first dose.	Each cohort will be comprised of three treatment periods (3 days each) with a follow up phone call at 48 hours after each dose.	Will be at least 10 days between doses for each participant.	Between 7 to 14 days following the final dose.	
 
 B	Each participant will receive up to 14 days of treatment with additional observation up to 96 hours after their final dose.	N/A	
 
 C	Each participant will receive up to 7 days of treatment.	N/A	
  
 
The total duration of the study will be approximately 11 weeks in Part A, approximately 9 weeks in Part B and approximately 8 weeks in Part C.
					Part	Screening	Treatment Period	Washout Period	Follow-Up	A	Up to 30 days before the first dose.	Each cohort will be comprised of three treatment periods (3 days each) with a follow up phone call at 48 hours after each dose.	Will be at least 10 days between doses for each participant.	Between 7 to 14 days following the final dose.	B	Each participant will receive up to 14 days of treatment with additional observation up to 96 hours after their final dose.	N/A	C	Each participant will receive up to 7 days of treatment.	N/A
Part	Screening	Treatment Period	Washout Period	Follow-Up																	
A	Up to 30 days before the first dose.	Each cohort will be comprised of three treatment periods (3 days each) with a follow up phone call at 48 hours after each dose.	Will be at least 10 days between doses for each participant.	Between 7 to 14 days following the final dose.																	
B		Each participant will receive up to 14 days of treatment with additional observation up to 96 hours after their final dose.	N/A																		
C		Each participant will receive up to 7 days of treatment.	N/A																		
Study intervention Assignment	
In Part A (Cohorts 1 and 2), each cohort has a crossover design with four treatment sequences that participants will be randomized to. Of the four sequences, three include placebo for one of the treatment periods whilst the last contains active for all treatment periods. This gives a 3:1 active:placebo ratio within each treatment period of the cohort (as shown below):
																				

Overview of Study Design and Key Features

	Treatment Period	Cohort 1				Cohort 2			
		(n=3)	(n=3)	(n=3)	(n=3)	(n=3)	(n=3)	(n=3)	(n=3)
1	A	A	A	P			-		
2	P	A	A	A			-		
3	A	P	A	A			-		
4			-		P	A	A	A	
5			-		A	P	A	A	
6			-		A	A	P	A	

Part B (Cohorts 3 and 4), follow a parallel group design where participants will be randomized in a 3:1 ratio (active:placebo) to receive study treatment.

Part C (Cohort 5) also follows a parallel group design with participants randomized in a 3:1 ratio (active:placebo) to receive study treatment. In addition, Part C will be stratified to ensure 8 SABA and/or intermittent ICS/LABA participants (6 active and 2 placebo) and 8 ICS or ICS/LABA participants (6 active and 2 placebo) are randomized.

Interim Analysis	There are no formal interim analyses conducted as part of this study, however the following in-stream analyses will be performed as described in the sections below.
Dose Escalation Committee	A review of preliminary safety, tolerability and plasma PK data will be conducted by the DEC prior to each dose level in Part A, before initiating repeat dosing in Part B, and before initiating repeat dosing asthmatics in Part C. Safety and tolerability data includes adverse event/serious adverse event (AE/SAE), clinical laboratory values, 12-lead electrocardiogram (ECG), vital signs and spirometry measurements. Additional details are available in the Dose Escalation Plan.
Instream Analysis of PK Data	Once each of Part A (Cohorts 1 and 2) and Part B (Cohorts 3 and 4) have completed, selected members of the GSK team will be formally unblinded to the treatment allocations of the completed participants for PK and safety data from these cohorts to enable the analysis and modelling of PK data to start. The aim of this analysis is to inform internal decision making around dose selection for future studies in the development plan of this compound. This analysis will not impact the conduct or the design of the current study and will be reported separately from this SAP.

2. SUCCESS CRITERIA

Given this study is the FTIH for GSK3923868, no formal statistical hypotheses will be tested. The primary objective is to evaluate the safety and tolerability of GSK3923868 in healthy participants and stable asthmatics.

3. ANALYSIS SETS

Analysis Set	Definition	Analyses Evaluated
Screened	All participants who were screened for eligibility.	Study Population
Enrolled	The All Subjects Enrolled (ASE) population will consist of all participants who enrolled in the study. Note: screening failures (who never passed screening even if rescreened) and participants screened but never enrolled into the study (Reserve, Not Used) are excluded from the Enrolled analysis set as they did not enter the study.	Study Population
Randomized	The randomized population will consist of all participants who were randomized including those randomized in error. A participant who is recorded as a screen failure and was also randomized will be considered as randomized in error provided that they have not performed any study assessments.	Study Population
Safety	All randomized participants who received at least 1 dose of study intervention. Participants will be analysed according to the treatment they received.	Safety
Pharmacokinetic (PK)	All randomized participants in the Safety population who had at least 1 non-missing PK assessment (Non-quantifiable [NQ] values will be considered as non-missing values). • Participants will be analysed according to the treatment they received.	PK

3.1. Definitions for Per Protocol Analysis Set

This study does not have a per protocol analysis set.

4. STATISTICAL ANALYSES

4.1. General Considerations

4.1.1. General Methodology

The Safety Analysis Set will be used for all outputs except for pharmacokinetic (PK) **CCI** endpoints which will use the Pharmacokinetic Analysis Set.

All cohorts will be presented separately, except Cohorts 3 and 4 which will be combined, unless otherwise stated. In addition, for Part A, all outputs excluding study population will be summarised according to treatment and dose level of GSK3923868.

In the case of wrong stratification assigned at the time of randomization, the analyses will be performed based on the data collected in the eCRF, not the assigned stratum at randomization.

Confidence intervals will use 95% confidence levels for both summary statistics and statistical analysis, unless otherwise stated.

Unless otherwise specified, continuous data will be summarized using descriptive statistics: n, mean, standard deviation (std), median, minimum and maximum. Categorical data will be summarized as the number and percentage of participants in each category.

4.1.2. Baseline Definition

For all endpoints the baseline value will be the latest pre-dose with a non-missing value, including day 1 pre-dose and those from unscheduled visits prior to the first dose of study treatment. For Part A, baseline will be defined as the latest pre-dose assessment at the start of each treatment period.

Baseline QTcF will be calculated as the average of the three pre-dose measurements on Day 1.

Unless otherwise stated, if baseline data is missing no derivation will be performed and baseline will be set to missing.

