**Footnotes to Part A: Single Ascending Dose | Healthy Participants (Cohort 1)**

1. Day -1 inhaler training may be performed on Day 1 if needed and before administration of the first dose. Additional training may be provided as needed and according to Investigator discretion.
2. To be performed according to local site procedures. Additional ad hoc testing may be implemented based on local site procedures.
3. No meals from 2 hours before dosing until 2 hours post dose.
4. Perform in triplicate and includes FEV1 and FVC.
5. Includes systolic and diastolic blood pressure, heart rate, respiration rate and tympanic temperature.
6. On Day 1 pre-dose of each treatment period, triplicate ECG measurements will be collected, and the mean values will be used to calculate baseline. At all other time points single ECGs will be taken.
7. Cardiac telemetry to start approximately 1-hour pre-dose and continuously until 6 hours post dose.

CCI

9. Clinical Chemistry and Haematology only.

CCI

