**Footnotes to Part C: Repeat Dose | Asthma (Cohort 5)**

1. Day -1 inhaler training may be performed on Day 1 if needed and before administration of the first dose. Additional training may be provided as needed and according to Investigator discretion.
2. To be performed according to local site procedures. Additional ad hoc testing may be implemented based on local site procedures.
3. Predose and 30 min only.
4. PEF measurements will be taken in triplicate twice each day (once in morning upon waking and once in the evening before bedtime) from Day -1 evening until discharge on Day 8. Clinical site staff will complete and record the PEF measurements at each time point.
5. Provide PEF device refresher training if necessary.
6. Includes systolic and diastolic blood pressure, heart rate, respiration rate and tympanic temperature.
7. Predose only
8. On treatment days ECGs will be collected at predose and 6-hours post-dose. On Day 1 predose, triplicate measurements will be collected, and the mean values will be used to calculate baseline. At all other times single ECGs can be taken.
9. Cardiac telemetry to start approximately 1-hour pre-dose and continuously until 6 hours post dose.
10. Clinical Chemistry and Haematology only.
11. At pre-dose, 5 min, 15 min, 30 min, 45 min, 1 h, 2 h, 4 h, 6 h, 8 h, 12 h and 16 h

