#### 8.1.3.2. 12-Lead Safety ECGs

- Safety ECGs will be performed in semi-supine position after at least 10 minutes rest.
- All safety ECGs must be obtained using an ECG machine that automatically calculates the heart rate and measures, PR, QRS, QT and QTcF intervals.
- Safety ECGs will be printed and interpreted on-site by the Investigator to ensure participant safety. Safety ECGs may also be printed from the Global Instrumentation (Manlius, NY, USA) M12R ECG continuous 12 lead digital recorder used for continuous cardiac monitoring (see Section 8.1.3.4). At time points where triplicate ECGs are required, the ECGs will be obtained at least 2 minutes apart and over a recording period of up to 10 minutes.
- Baseline QTcF will be based on the average of 3 predose ECGs collected on Day 1 (in Part A, Day 1 predose for each treatment period should be considered as baseline).
- Refer to Section 7.2.4 for QTc specific stopping criteria.
- Refer to the SRM for further information.

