4.2.2.2. Laboratory Data, Vital Signs, ECGs and Spirometry

For laboratory data, separate tables for haematology, clinical chemistry and urinalysis tests will be produced. Liver biochemical parameters will be included with clinical chemistry tests. Vital signs data will include semi supine systolic and diastolic blood pressure, pulse rate, respiratory rate and temperature measurements.

ECG data will include PR, QRS, QT and QTcF intervals.

Spirometry data will include FEV₁ and FVC measurements.

For haematology, clinical chemistry, urinalysis, vital signs, ECG and spirometry data the following information will be summarised:

1. Clinically significant values at each visit
2. Raw and change from baseline values at each visit

Note: The first table is the only one included as part of the primary endpoint. [redacted]

[redacted]

In order to detect potential bronchospasms, an additional table for spirometry values will be produced which summarises the changes between daily pre- and post-dose FEV₁ and FVC values.

For ECGs, a figure plotting the baseline QTcF and the worst-case post-baseline values will be produced. The figure will have reference lines at 480 and 500 msec for both the ordinate and the abscissa axes. There will be diagonal reference lines at equality (i.e. a 45 degree line), at equality plus 30 msec, and at equality plus 60 msec.

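### SAP 4.1.2 averages the Day 1 pre-dose triplicate ECG for QTcF only; read literally, PR, QRS and QT get a noisier baseline than the protocol's schedule footnotes call for

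*SAP*

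**What the plan says.** SAP 4.1.2 gives a rule meant to cover everything: "For all endpoints the baseline value will be the latest pre-dose with a non-missing value". For the crossover part it adds: "For Part A, baseline will be defined as the latest pre-dose assessment at the start of each treatment period". It then treats one ECG parameter separately: "Baseline QTcF will be calculated as the average of the three pre-dose measurements on Day 1". PR, QRS and QT have no rule of their own.

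SAP 4.2.2.2 sets the scope of the ECG analysis: "ECG data will include PR, QRS, QT and QTcF intervals". For these it plans two summaries at each visit: clinically significant values, and raw values with change from baseline. Only the first belongs to the primary endpoint.

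The protocol's Schedule of Activities (Section 1.3) handles the ECG baseline in footnotes. For both Part A cohorts: "On Day 1 pre-dose of each treatment period, triplicate ECG measurements will be collected, and the mean values will be used to calculate baseline". For Part C: "On Day 1 predose, triplicate measurements will be collected, and the mean values will be used to calculate baseline". The Part B footnote reads the same way as Part C. None is restricted to QTcF. Elsewhere in the schedule the recordings are single; in Part A, "At all other time points single ECGs will be taken".

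The protocol's body text is narrower. Section 8.1.3.2 says "Baseline QTcF will be based on the average of 3 predose ECGs collected on Day 1", and Section 7.2.4 repeats this for the QTc stopping criteria. Neither says how the other intervals are handled. SAP 4.7 states that nothing departs from the protocol's planned analysis.

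**The concern.** Three tracings are recorded before dosing so that the baseline can be averaged. If the SAP is programmed as written, that happens for QTcF alone, and the PR, QRS and QT baselines rest on one of the three tracings. There are three consequences.

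- The SAP and the schedule footnotes give different baselines for the same data, and the SAP does not declare a difference.
- Changes in PR, QRS and QT carry more measurement noise than they need to. The groups on active drug are small (9 per dose in Part A, 12 in each of Parts B and C), and SAP 4.1.1 reports minimum and maximum, so a stray baseline reading shows directly in the table.
- QT and QTcF come from the same tracings but would have baselines built in two ways, so a participant's QT and QTcF changes are not like for like.

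**Working it through.** The documents state no figure for this, so there is nothing to reproduce. The check has two parts.

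**1. The texts side by side**

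| Source | Parameters covered | Baseline |
|---|---|---|
| SAP 4.1.2, general rule | all endpoints | latest non-missing pre-dose value |
| SAP 4.1.2, exception | QTcF | mean of three |
| Protocol 1.3 footnotes, Parts A, B, C | ECG, no restriction | mean of triplicate |
| Protocol 7.2.4 and 8.1.3.2 | QTcF | mean of three |

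The sources agree on QTcF. For PR, QRS and QT, the footnotes and the general SAP rule differ, and the protocol's body sections are silent.

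**2. The size of the extra noise**

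Let σ² be the variance between replicate ECGs on one occasion and τ² the variance between occasions. Protocol 8.1.3.2 takes a triplicate within about 10 minutes, so it is reasonable to let the three readings share one occasion term. The post-dose reading is single.

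- Single baseline reading: Var(change) = 2τ² + 2σ²
- Mean of three: Var(change) = 2τ² + σ² + σ²/3
- Reduction in SD = 1 − √[(2τ² + 4σ²/3) / (2τ² + 2σ²)]

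The documents give neither variance, so τ²/σ² is an assumption and is varied. Variances are in units of σ².

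| τ²/σ² | Single | Mean of three | Variance ratio | SD ratio | SD reduction |
|---|---|---|---|---|---|
| 0 | 2.00 | 1.33 | 1.50 | 1.22 | 18.4% |
| 0.25 | 2.50 | 1.83 | 1.36 | 1.17 | 14.4% |
| 0.5 | 3.00 | 2.33 | 1.29 | 1.13 | 11.8% |
| 1 | 4.00 | 3.33 | 1.20 | 1.10 | 8.7% |
| 2 | 6.00 | 5.33 | 1.13 | 1.06 | 5.7% |
| 3 | 8.00 | 7.33 | 1.09 | 1.04 | 4.3% |

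The first row is a ceiling: 1 − √(1.333/2) = 1 − 0.816 = 18.4%. It needs no variation at all between occasions. Post-dose ECGs run from 5 minutes after dosing in Part A to Day 18 in Part B, so the lower rows are more plausible for most visits. If the three replicates are exchangeable, the last reading and the mean have the same expectation, so the issue is precision and not bias.

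**The case against.** The strongest defence is that the SAP never says a single reading is used or that two are discarded. A scheduled triplicate can be regarded as one assessment, and the Part A sentence speaks of the latest assessment. SAP Section 1 leaves further data-handling detail to the Output and Programming Specification, which is not among these documents. That reading is possible. It sits less well with the general rule, which speaks of a value, and with the QTcF sentence, which would be unnecessary if averaging were already implied. What stands is that the single-reading baseline is the literal reading and not a certainty.

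Second, the SAP matches what protocol 7.2.4 and 8.1.3.2 say about QTcF. A reader might infer that the SAP overturns a protocol-wide rule. The documents do not support that: the conflict is with the schedule footnotes, and the body sections set no rule for the other intervals.

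Third, a reader might infer that the primary endpoint or the QTc decisions are affected. The documents do not show this. QTcF is averaged already, and it is the interval used in the QTc stopping criteria and in the SAP's plot of baseline against worst post-baseline value. The change table is outside the primary endpoint, no hypotheses are tested, and neither document gives a threshold on change in PR, QRS or QT. The ranges of potential clinical interest are left to the Output and Programming Specification.

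Fourth, requiring all three readings could do harm. SAP 4.1.2 sets baseline to missing when baseline data are missing, so a strict mean-of-three rule could drop a participant whom the present rule keeps. This objection is right, and the fix must deal with it.

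**Conclusion.** The point holds in a limited form. Read literally, SAP 4.1.2 gives PR, QRS and QT a baseline that differs from the one in the protocol's schedule footnotes, and the difference is undeclared. The cost is avoidable noise in descriptive change-from-baseline summaries, plus baselines for QT and QTcF that are built differently. Averaging would lower the SD of change by 18% at most, and by about 9% or 4% if between-occasion variance is one or three times the replicate variance. These figures assume equal replicate variance before and after dosing, independent replicate errors and single post-dose readings. It would go too far to quote 18% as the expected gain or to treat the safety conclusions as compromised. The correction is worth making because the readings are collected anyway.

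**What to change.** In SAP 4.1.2, replace the QTcF sentence with a rule for every 12-lead ECG parameter:

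- Baseline is the mean of the available Day 1 pre-dose triplicate readings, taken separately for each treatment period in Part A.
- If only one or two of the three are available, use those.
- If none is available, use the latest earlier pre-dose ECG.
- The latest pre-dose rule stays for all other endpoints.

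The second and third points also settle incomplete triplicates for QTcF, on which the present sentence is silent. The Output and Programming Specification should carry the same rule.

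The cost is a few lines of SAP text and the matching programming. No procedure, visit or participant burden changes. With the fallback in place, no participant who has a baseline under the general rule loses it.
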